### **5.11. Pharmacokinetic/Pharmacodynamic Analyses**

Pharmacokinetic (PK) and pharmacodynamic analyses will be performed according to a separate PK analysis plan.

### **5.12. Biomarker Analyses**

The biomarkers of interest (e.g., *BRCA* status based on the local or central lab) will be summarized. The association between biomarkers and clinical outcomes will be explored. Further exploratory analysis of biomarkers may be conducted if deemed necessary and a sufficient number of patients who express the biomarker(s) are available.

### **5.13. Safety Analyses**

Safety analyses will be based on the safety population. Safety analyses will be summarized by cohort and overall.

#### **5.13.1. Extent of Exposure**

Study drug exposure information will be summarized by cohort and overall, including cycles received per subject, duration on therapy, cumulative dose ( $\text{mg}/\text{m}^2$ ), dose intensity and relative dose intensity.

Prexasertib will be administered as an intravenous infusion on Day 1 and 15 of a 28-day cycle. Duration on therapy is calculated as the last dosing date+14-first dosing date. Dose intensity of prexasertib ( $\text{mg}/\text{m}^2/\text{week}$ ) is calculated as cumulative dose/ duration on therapy in weeks. Relative dose intensity of prexasertib is calculated as actual dose intensity per week/planned dose intensity per week  $\times 100$ , where planned dose intensity per week= $(105/2) \text{ mg}/\text{m}^2/\text{week}$ .

Dose adjustments, delays and omissions, along with the reasons, will be summarized and listed.

### **5.13.2. Adverse Events**

Adverse event (AE) verbatim terms will be provided by the investigators and then will be mapped by Lilly or its designee to corresponding terminology within the Medical Dictionary for Regulatory Activities (MedDRA) Lower Level term (LLT) dictionary. The investigator will use Common Terminology Criteria for Adverse Events (CTCAE) version 4.0 (NCI 2009) to assign AE severity grades.

Pre-existing conditions are defined as AEs that begin but do not resolve prior to the first dose of study drug in each study period. Pre-existing conditions will be presented by patient and can be combined with the listing of AE, so that the history of the pre-existing conditions/AEs can be traced.

A treatment emergent adverse event (TEAE) is defined as any AE that begins on or after the day of first dose in the reporting study period or any pre-existing condition that increases in CTCAE grade on or after the day of first dose in the reporting study period. The MedDRA LLT will be used in the treatment-emergent computation.

The number of patients who experienced a TEAE, or TEAE possibly related to study drug, will be summarized. Treatment-emergent adverse events will be summarized by SOC, by Preferred Term (PT) of decreasing frequency within SOC, and by maximum CTCAE grade and grade categories (any, Grade 3 or higher).

### **5.13.3. Deaths, Serious Adverse Events, Other significant Adverse Events**

All deaths that occur during the study, within 30 days of the study treatment discontinuation, as well as the cause of death, will be summarized and listed.

Serious adverse events (SAEs) are those events that result in death, are life-threatening, require or prolong hospitalization, result in persistent or significant disability/incapacity, or cause congenital anomaly/birth defect. Serious adverse events will be tabulated by SOC, PT terms, and relationship to study drug.

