9.2.1. Serious Adverse Events

An SAE is any AE from this study that results in one of the following outcomes:

- death
- initial or prolonged inpatient hospitalization
- a life-threatening experience (that is, immediate risk of dying)
- persistent or significant disability/incapacity

- congenital anomaly/birth defect
- important medical events that may not be immediately life-threatening or result in death or require hospitalization may be considered serious when, based upon appropriate medical judgment, they may jeopardize the patient and may require intervention to prevent one of the other outcomes listed in the definition above.

Although all AEs after signing the ICF are recorded by the site in the CRF/electronic data entry, SAE reporting to Lilly begins after the patient has signed the ICF and has received prexasertib. However, if an SAE occurs after signing the ICF, but prior to receiving prexasertib, it needs to be reported ONLY if it is considered reasonably possibly related to study procedures.

Study site personnel must notify Lilly or its designee of any SAE within 24 hours of investigator awareness of the event via a Lilly-approved method. If alerts are issued via telephone, they are to be immediately followed with official notification on study-specific SAE forms. This 24-hour notification requirement refers to the initial SAE information and all follow-up SAE information.

Pregnancy (during maternal exposure to prexasertib) does not meet the definition of an AE but should be reported. However, to fulfill regulatory requirements any pregnancy should be reported following the SAE process to collect data on the outcome for both mother and fetus.

Investigators are not obligated to actively seek AEs or SAEs in patients once they have discontinued and/or completed the study (the patient summary CRF has been completed). However, if the investigator learns of any SAE, including a death, at any time after a patient has been discharged from the study, and he/she considers the event reasonably possibly related to the study treatment or study participation, the investigator must promptly notify Lilly.

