10.3.2. Safety Analyses

All patients who receive ≥ 1 dose of prexasertib will be evaluated for safety and toxicity.

The Medical Dictionary for Regulatory Activities (MedDRA[®]) Version 20.0 (or higher) will be used when reporting AEs by MedDRA terms. The MedDRA LLT will be used in the treatment-

emergent computation. Adverse events will be summarized by System Organ Class (SOC) and by decreasing frequency of Preferred Term (PT) within SOC. CTCAE version 4.0 will be used to report AE severity grades.

Safety analyses will include summaries of the following:

- AEs, including severity and possible relationship to study drug
- SAEs, including possible relationship to study drug
- AEs leading to dose adjustments
- discontinuations from study treatment due to AEs or death
- treatment emergent abnormal changes in laboratory values
- treatment emergent abnormal changes in vital signs and ECGs.

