10.3.3.10. Healthcare Resource Utilization

Hospitalizations, transfusions, ED visits, SBO, and concomitant medications during study treatment will be summarized by cohort.

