### **5.13.6. Electrocardiograms**

Local electrocardiograms (ECGs) will be summarized by cycle and overall. The summary by cycle will classify patients as having normal or abnormal. Additionally, QT, RR, and QRS

intervals will also be collected and QTcF will be calculated based on these parameters. Adverse events that could be associated with abnormal ECGs will be presented, if appropriate.

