### **5.13.7. Healthcare Resource Utilization**

The frequency and percentage of patients with hospitalizations, transfusions, ED visits experienced during the study treatment period or 30-day post discontinuation follow-up period will be summarized.

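### The SAP's SAE definition lacks one of the protocol's six seriousness criteria, and two safety outputs the protocol promises (treatment-emergent ECG change, small bowel obstruction by cohort) are not specified

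*SAP*

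**What the plan says.** **Serious adverse events.** SAP 5.13.3 reads "Serious adverse events (SAEs) are those events that result in death, are life-threatening, require or prolong hospitalization, result in persistent or significant disability/incapacity", and the list closes with "or cause congenital anomaly/birth defect. Serious adverse events will be tabulated by SOC, PT terms, and relationship to study drug". Protocol 9.2.1 has the same five outcomes plus a sixth: "important medical events that may not be immediately life-threatening or result in death or require hospitalization may be considered serious when", in medical judgment, they may jeopardize the patient and may need intervention to prevent one of the other outcomes.

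**ECGs.** Protocol 10.3.2 lists among its safety summaries "treatment emergent abnormal changes in vital signs and ECGs". SAP 5.13.6 summarizes local ECGs by cycle and overall: "The summary by cycle will classify patients as having normal or abnormal". It adds that QT, RR and QRS intervals are collected and QTcF is calculated from them, and that AEs possibly linked to abnormal ECGs are presented if appropriate.

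**Small bowel obstruction.** Protocol 9.9 collects SBO in support of the safety assessment. Protocol 10.3.3.10 commits to a summary: "Hospitalizations, transfusions, ED visits, SBO, and concomitant medications during study treatment will be summarized by cohort". SAP 5.13.7 has "The frequency and percentage of patients with hospitalizations, transfusions, ED visits experienced during the study treatment period" or the 30-day follow-up. SBO is named nowhere in the SAP.

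**The concern.** The SAP is the document from which the tables are programmed. Where it is narrower than the protocol, the report can end up with less than the protocol committed to without anyone having decided so. Safety is a secondary objective of this single-agent study, and the three gaps touch different parts of it.

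- **SAE definition.** The criterion left out is the one for events that count as serious without death, immediate threat to life or admission. A programmer who applied the SAP sentence literally would not count an event reported as serious on that ground alone.
- **ECG.** A normal/abnormal class not referred to baseline treats a long-standing abnormality like a new one. A calculated QTcF with no planned display answers no question. The protocol treats QT as a concern: exclusion [23] sets a screening QTcF limit of 480 msec, and section 7.7 has advice on QT-prolonging co-medication on dosing days.
- **SBO.** The protocol collects it on purpose and promises a by-cohort summary, for which the SAP plans no table.

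**Working it through.** There is no plan figure to reproduce, and the point rests on no rate, power or sample size. The check sets the texts side by side.

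**Step 1: seriousness criteria**

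| Criterion | Protocol 9.2.1 | SAP 5.13.3 |
|---|---|---|
| Death | yes | yes |
| Life-threatening | yes | yes |
| Hospitalization, initial or prolonged | yes | yes |
| Disability/incapacity | yes | yes |
| Congenital anomaly/birth defect | yes | yes |
| Important medical event | yes | no |

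Count: 6 − 5 = 1 criterion missing. The SAP list is closed, with no wording such as *for example*, and the SAP does not say that the investigator's serious flag decides.

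**Step 2: where a literal reading would lead**

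Take an event that the site reports as serious only because it is an important medical event.

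- SAP 5.13.3: it would be missing from the SAE table.
- SAP 5.16: the SAE listing and summary for the Investigator's Brochure would carry the same count.
- SAP 5.17 (registry): serious AEs count whether or not treatment-emergent, while the Other category needs an event that is both treatment-emergent and not serious. If treatment-emergent, the event would move to Other, where terms under 5% in every group may be left out. If not treatment-emergent, it would fall in neither category.
- SAP 5.13.2: if treatment-emergent, it would still be in the TEAE tables by preferred term and maximum grade.

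**Step 3: ECG time points against the planned display**

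The on-treatment schedule (protocol Table JTJN.2) gives these scheduled ECGs per patient:

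- Cycle 1: Day 1 predose, Day 1 within 15 minutes after end of infusion, Day 15 predose = 3
- Cycle 2: the same = 3
- Cycle 3 onward: Day 1 and Day 15, each predose = 2 per cycle

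The scheduled end-of-infusion ECGs are therefore 1 + 1 = 2 per patient, each with a same-day predose ECG. SAP 5.13.6 gives no rule for turning three ECGs into one class for Cycle 1 or Cycle 2, and does not ask for the two kinds of time point to be kept apart. It specifies no change from baseline, no shift, no categories and no paired difference. SAP 5.1 does define a safety baseline, and SAP 5.13.4 uses shift tables from baseline for laboratory values, so the missing element is specific to ECGs.

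**Step 4: SBO**

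Protocol 10.3.3.10 names five items: hospitalizations, transfusions, ED visits, SBO and concomitant medications. SAP 5.13.7 names three, and 5 − 3 = 2. Of those two, concomitant medications are covered in SAP 5.7. SBO is the one item without a dedicated output.

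**Step 5: can timing explain it?**

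The SAP was approved on 02-Apr-2018 and protocol amendment (b) on 17-Sep-2018. That amendment's list of changes does not include protocol 9.2.1, 9.9, 10.3.2 or 10.3.3.10, so it does not explain the differences.

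**The case against.** The strongest reply is that little is lost. Sites report SAEs under protocol 9.2.1 with all six criteria, and the SAP sentence may be only a short description of events already flagged as serious. Nothing says that seriousness is re-derived. This stands in part: the undercount is conditional. But nothing says that the site's flag governs either, and a closed definition followed by an instruction to tabulate can be programmed as written.

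Second, a reader might infer that the named risks vanish from the safety results. The documents do not support that. SBO is gathered through AE collection, and SAP 5.13.2 tabulates all TEAEs by term and grade. Cytopenias also appear in the laboratory shift tables (SAP 5.13.4), and transfusions and admissions are counted in SAP 5.13.7. This part of the reply stands in full. It does not replace the SBO summary promised by cohort. The SAE table is not a sure substitute either, because protocol 9.2.1 keeps SAEs caused by progression out of reporting unless they are possibly related to prexasertib.

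Third, ECGs are not reduced to normal/abnormal alone: intervals are collected, QTcF is calculated, and ECG-related AEs may be shown. That is correct. The gap is that no QTcF summary is specified. A TEAE table shows a QT effect only when an investigator records it as an AE, and it cannot show a change in QTcF.

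Fourth, a reader might try to size the SAE loss from the earlier NCI-sponsored study quoted in protocol 3.2.2.3 (Grade 4 neutropenia in 69%, febrile neutropenia in 6%). Those figures do not say how many events were reported as serious or on what ground, so they measure no loss.

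**Conclusion.** The point holds as three mismatches between SAP and protocol: one in a definition, two in planned outputs.

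- **SAE definition:** 5 of 6 criteria are kept. If the SAP text is used to derive or filter seriousness, the SAE tables and the registry split undercount; if the investigator-reported flag is used, they do not. The documents do not say which applies, and the size of any undercount cannot be derived from them.
- **ECG:** the treatment-emergent changes promised in protocol 10.3.2 are not delivered by SAP 5.13.6 as written, and the two scheduled predose/end-of-infusion pairs per patient yield no planned QTcF change.
- **SBO:** the by-cohort summary promised in protocol 10.3.3.10 is missing from the SAP.

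The consequence is a possible undercount and two missing outputs, not loss of these risks from the results. The primary endpoint and the numerical futility rules are untouched.

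**What to change.** - **SAP 5.13.3:** adopt the six criteria of protocol 9.2.1, or state that the investigator-reported serious flag under 9.2.1 governs every SAE output, including those in SAP 5.16 and 5.17.
- **SAP 5.13.6:** present normal/abnormal as a shift from baseline. Add QTcF change from baseline by time point, the paired change from predose to end of infusion on Day 1 of Cycles 1 and 2, and a categorical summary of maximum QTcF that includes the protocol's own 480 msec value. Any other cut-offs are for the sponsor to choose and state in advance.
- **SAP 5.13.7:** add SBO, by cohort.

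The cost is revised wording and a few extra tables from data already collected. The SAE count could look slightly less favourable. The SAP needs a revision in any case, because its timing of the primary analysis (SAP 5.1) no longer matches the amended protocol 10.3.

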### **5.13.4. Clinical Laboratory Evaluation**

All relevant hematology and chemistry laboratory values will be graded according to CTCAE Version 4. Shift tables showing the change from baseline to the worst grade on study will be presented.

### **5.13.5. Vital Signs and Other Physical Findings**

Temperature, blood pressure, pulse rate, weight and ECOG performance score will be summarized by cohort and overall.

### **5.13.6. Electrocardiograms**

Local electrocardiograms (ECGs) will be summarized by cycle and overall. The summary by cycle will classify patients as having normal or abnormal. Additionally, QT, RR, and QRS

intervals will also be collected and QTcF will be calculated based on these parameters. Adverse events that could be associated with abnormal ECGs will be presented, if appropriate.

### **5.13.7. Healthcare Resource Utilization**

The frequency and percentage of patients with hospitalizations, transfusions, ED visits experienced during the study treatment period or 30-day post discontinuation follow-up period will be summarized.

## **5.14. Protocol Violations**

Significant protocol violations that potentially compromise the data integrity and patients' safety will be summarized by cohort and overall. These violations will include deviations which can be identified programmatically and those which can only be identified by the clinical research associate (CRA) during monitoring. Significant protocol deviations are described in another document within the study Trial Master File.

## **5.15. Interim Analyses**

Interim analyses will be conducted regularly to evaluate closing enrollment early due to futility. For each cohort, the first futility interim analysis will be conducted after approximately 20 patients have been treated and completed  $\geq 2$  cycles or have discontinued before the first post-baseline tumor assessment. The interim analysis may be potentially delayed if the confirmation of response is required. The futility rule is based on the posterior probability of activity via a Bayesian model. A cohort will be closed if the posterior probability is less than the prespecified futility threshold (e.g., 20% probability ORR exceeds the prespecified threshold of activity). Borrowing of information across cohorts may be allowed, and the strength of borrowing may depend on the similarity between the cohorts. The prior distribution of response rate used in the model will be derived from the ongoing NCI-sponsored Phase 2 Study E001 (NCT02203513). The futility rules for each cohort are described as follows:

- Cohorts 1 to 3 (platinum-resistant):  $\Pr(\text{ORR} > 25\%) < 20\%$
- Cohort 4 (platinum-refractory):  $\Pr(\text{ORR} > 15\%) < 20\%$ .

It is planned that enrollment can continue while interim analyses are conducted, but the sponsor may decide to pause the enrollment, if necessary. For the cohorts that can continue after the evaluation of the first 20 patients, subsequent interim analyses will occur after approximately every 20 additional patients. The interval between interim analyses may be adjusted if deemed appropriate based on enrollment rates and available data. At each subsequent interim for each cohort, the posterior probability of response rate will be updated based on the available data and a higher futility threshold for the posterior probability may be adopted if deemed appropriate by the sponsor (e.g., 40% probability ORR exceeds the prespecified threshold of activity).

At each interim analysis, although the decision of whether to continue a cohort will be made primarily based on the futility rules, the totality of data (including safety, efficacy, PK, and biomarker data, if available) will also be reviewed and considered in the final decision made by the sponsor. The decision will be communicated to sites in writing if the sponsor determines a

cohort is to be closed. The evaluation of efficacy may be based on all treated patients with centrally confirmed *BRCA* mutation status if available. Other interim analyses may be conducted if deemed appropriate by the sponsor. The interim analyses may be combined if they are expected to occur within a similar timeframe; interim analyses may also be combined with any prespecified safety review or annual reporting (such as an update to the IB or Development Safety Update Review, etc.).

### 5.16. Annual Report Analyses

The following reports are needed as requested for annual reporting purposes.

Development Safety Update Report:

- Cumulative Subject Exposure by Age Group and Sex
- Cumulative Subject Exposure by Racial Group
- Estimated Cumulative Subject Exposure
- Exposure Information
- Listing of Discontinuations Due to AE During the Reporting Period
- Listing of Subjects Who Died During the Reporting Period

Clinical Investigator's Brochure (IB):

- Listing and Summary of SAE
- Listing and Summary of Death
- Listing and Summary of TEAE (and by maximum CTCAE grade)
- Listing and Summary of Patient Disposition
- Listing and Summary of Study Drug Adjustment

Other reports may be requested if deemed appropriate for the IB.

### 5.17. Clinical Trial Registry Analyses

Additional analyses will be performed for the purpose of fulfilling the Clinical Trial Registry (CTR) requirements.

Analyses provided for the CTR requirements include the following:

- Summary of AEs, provided as a dataset which will be converted to an XML file. Both SAEs and 'Other' AEs will be summarized by: MedDRA PT within treatment group.
- An AE is considered 'Serious' whether or not it is a TEAE.

- An AE is considered in the ‘Other’ category if it is both a TEAE and is not serious. For each SAE and ‘Other’ AE, for each term and treatment group, the following are provided:
  - the number of participants at risk of an event
  - the number of participants who experienced each event term
  - the number of events experienced.
- Consistent with [www.ClinicalTrials.gov](http://www.ClinicalTrials.gov) requirements, ‘Other’ AEs that occur in fewer than 5% of patients/subjects in every treatment group may not be included if a 5% threshold is chosen (5% is the minimum threshold).
- Adverse event reporting is consistent with other document disclosures for example, the clinical study report (CSR), manuscripts, and so forth.

In addition, a participant flow will be created that will describe how many enrolled patients completed the study, and for those who did not, the frequency of each reason for not completing. This analysis will be based on study discontinuation, not treatment discontinuation. A patient will be identified as having completed the study if the patient has received  $\geq 1$  dose of study drug and have  $\geq 1$  post-baseline tumor assessment at the time of the final analysis.

